2.1 Description of the Investigational Device

HidraMed Solutions has developed an adhesive free wound dressing fixation device for people living with Hidradenitis Suppurativa (HS), a chronic and debilitating disease which causes non-healing lesions of the skin, mainly in the armpit, groin, thigh and buttocks - Hidrawear AX, designed to make dressing changes quick and easy for subjects.

The Hidrawear AX is designed to improve the wound care management for HS and chronic wound subjects. The unique features of the product completely remove the use of adhesives on the skin. Designed by a patient, for patients, Hidrawear AX provides comfort, ease of use and effective care for the every-day management of HS lesions.

The 3- part system is comprised of

- 1. The investigational device: the Hidrawear AX: A washable garment
- 2. An off-the-shelf dressing
- 3. An off-the-shelf mechanism to attach the dressing to the Hidrawear AX, such as a fastener supplied with the dressing or medical tape

The body conforming garment acts as a second skin and incorporates largely perforated panels over wound affected areas, minimising skin contact and aerating the area. The main function of the perforated is to act as a retaining device for the wound pads.

[figure not shown]

[figure not shown]
CE-GAX001-01

V4.0

CR: 144

The garment facilitates easy insertion, removal, precise positioning and adjustment of a non-adhesive wound dressing onto the effected wound space. The perforated section of the garment sits on the outer surface of the dressing providing provisional fixation. Next, an outer patch is placed on the outside of the garment on the footprint of the dressing. Through a hook and loop mechanism the dressing is now fully secured in place. It is designed so that quick, precise and pain free dressing changes can be achieved in less than 15 seconds

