2.3 Intended Purpose

Is intended for the retention of a dressing in the axilla area.

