3.4 Clinical Evaluation

This pilot study will evaluate usability - the safety, efficacy and performance of HidraWear AX in the home setting. Quality of life, ease of use and comfort of Hidrawear AX will be assessed.

The clinical effect of the wound pad will not be assessed. HldraWear AX does not claim wound healing but is a quicker and easier way to dress wounds.

CE-GAX001-01

V4.0

CR: 144

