5.3 Claims of Performance

Easy to use.

Comfortable.

Faster than existing products used.

Reduces pain.

Secure dressing retention

CE-GAX001-01

V4.0

CR: 144

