6.1.3 Primary and Secondary Endpoints

Primary Endpoint

• The change in the ease of use at week 3 compared to Day 0

Secondary Endpoints - Subject Assessment

- Ease of use W2 vs W1
- Comfort measured on a 10 point scale D21 vs D0
- Pain measured on a 10 point scale D21 vs D0
- Time measured on a 10 point scale D21 vs D0
- Dressing retention confidence measured on a 10 point scale D21 vs D0

Secondary Endpoints – Nurse Assessment

- Necessity to stretch/contort the body to apply dressing
- Did subject need assistance
- Could dressing be applied without raising arms over head
- Additional equipment used- mirror, scissors etc.

Outcome selection rationale:

- Assessment of ease of use as primary outcome was selected as most users have voiced frustration
- Comfort was selected as we wish to learn if Hidrawear AX is comfortable to use.
- Dressing retention confidence was selected as user have voiced frustration
- Dressing related pain was selected as HidraWear AX may reduce unnecessary patient distress due to dressing/adhesive related pain
- Time was selected as regular wound dressing changes are time consuming (6)

CE-GAX001-01

V4.0

CR: 144

DLQI was selected as it a validated tool that has been commonly used for assessment of quality of life for HS subjects. will assess if Hidrawear AX is better than the current products used by HS subjects.

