10. Have you ever had a dressing leak/move or fall off? Yes/No

11. How long do you typically spend doing dressing changes and tending to your lesions on a daily basis?

0-5	6-10	11-15	16-20	21-25	26-30	31-35	36-40	41-45	Over 45
minutes									

- 12. Do you think that your wound care needs are being met by current dressing options? Yes/no/maybe (please elaborate)
- 13. How satisfied are you with current dressings in terms of

Comfort - scale 0-10

Ease of application, adjustment and removal (a full dressing change) – scale 0-10

Confidence it won't leak, move or fall off scale 0-10

- 14. Do you believe that wound care / dressing changes are a contributing factor to a reduced quality of life for you? Yes/No/Don't Know
- 15. Does managing your wounds / dressings impact negatively on:

Work life yes/no Social life and hobbies yes/no Sex and relationships yes/no Day to day activities yes/no Mental health yes/no Financial well being yes/no

General wellbeing yes/no

16. Please tell us, in your own words about your experiences of home management/ dressings for HS. How does it make you feel?

For example- What is your biggest frustration with dressings? Does it impact your daily life? Any problems you experience when doing your dressing changes. Do you need a mirror, extra equipment, assistance? What is the worst part about it and how do you manage on a daily basis?

Section 4: HS information and Support

CE-GAX001-01

V4.0

CR: 144

1. Where do you find your information on HS?

Doctors/	Information	Online patient	Meeting other	Other (please
Healthcare Websites		forums/groups	patients	specify in
				comment)

2. What do you think would help you feel more supported in managing your HS? What would you like to see? Please elaborate in comments.

Thank you for participating in our survey. Your time and effort will directly contribute to the publication that highlights the daily impact of HS wounds and wound care on the patient's life.

If some of the questions have made you feel upset about your HS, please visit the following sites for information and support:

https://irishskin.ie/ask-our-dermatology-nurse/

https://hopeforhs.org/

CE-GAX001-01

V4.0

CR: 144

21 APPENDIX 3 – SUBJECT ASSESSMENT FORM DAY 0

Subject Assessment Day 0

[figure not shown]
Please dress your wound using your usual product and method.

While you are dressing your wound, please pay close attention to the following:

[figure not shown]
- How easy/difficult it is

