- Is it time consuming for a full dressing change
- How comfortable/uncomfortable is a dressing change
- Do you experience dressing related pain
- How confident are you that your dressing will not leak or move.

Once the dressing change is complete, please answer the following:

1. Is it easy/difficult to change your dressing using your current product and method? Please indicate the level of difficulty involved.

2. How time consuming is a dressing change using your current product and method?

Page 45 of 56

[figure not shown]
The Master Copy of this document is electronically approved and maintained as an electronic record

CE-GAX001-01 V4.0

CR: 144

[figure not shown]
3. How Comfortable is it to use and wear your current dressing?

4. Do you require pain killers before a dressing change? Please tick

Yes	No

5. Do you experience dressing related pain using current product?

[figure not shown]

CE-GAX001-01

[figure not shown]
V4.0

CR: 144

6. How confident are you that your current dressing will not leak or move?

7. How confident do you feel in yourself about your body image – self confidence/self esteem?

CE-GAX001-01

V4.0

CR: 144

22 APPENDIX 4 – SUBJECT ASSESSMENT FORM DAY 21

[figure not shown]
Please dress your wound using HidraWear AX

While you are dressing your wound, please pay close attention to the following:

[figure not shown]
- How easy/difficult it is
- Is it time consuming for a full dressing change
- How comfortable/uncomfortable is a dressing change
- Do you experience dressing related pain
- How confident are you that your dressing will not leak or move.

Once the dressing change is complete, please answer the following:

8. Is it easy/difficult to change your dressing using HidraWear AX? Please indicate the level of difficulty involved.

9. How time consuming is a dressing change using HidraWear AX?

Page 48 of 56

The Master Copy of this document is electronically approved and maintained as an electronic record

[figure not shown]

CE-GAX001-01

V4.0

CR: 144

[figure not shown]
10. How Comfortable is it to use and wear HidraWear AX?

11. Do you require pain killers before a dressing change? Please tick

Yes	No		

12.
Do you experience dressing related pain using HidraWear AX?

[figure not shown]

CE-GAX001-01

[figure not shown]
V4.0

CR: 144

13. How confident are you that HidaWear AX will not leak or move?

14. How confident do you feel in yourself about your body image – self confidence/self esteem?

CE-GAX001-01

V4.0

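### The retention endpoint is scored by one item that joins leaking and moving, so a change in it cannot show whether the dressing stayed in place better or leaked less

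*Combined protocol and SAP*

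**What the plan says.** **Purpose and mechanism.** Section 2.3 gives the device's purpose: "Is intended for the retention of a dressing in the axilla area". Section 2.1 speaks of position and fixation: "The main function of the perforated is to act as a retaining device for the wound pads", and "Through a hook and loop mechanism the dressing is now fully secured in place".

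**Claim and endpoint.** Retention is a secondary objective (5.1), part of the hypothesis (5.2) and a claim of performance (5.3, "Secure dressing retention"). Section 6.1.3 makes it a subject-rated secondary endpoint: "Dressing retention confidence measured on a 10 point scale D21 vs D0".

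**The item.** Appendix 3, item 6 (Day 0) asks "How confident are you that your current dressing will not leak or move". Appendix 4, item 13 (Day 21) joins leaking and moving in the same way but asks about HidraWear AX instead of the dressing. Section 6.1.4 says confidence is also asked at Days 7 and 14; the appendices do not print that wording.

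**The survey.** In Appendix 2, Section 3, question 13 also uses one combined rating, with falling off added: "leak, move or fall off scale 0-10". Section 3.1 plans a comparison between the patients' experience and the survey data.

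**The concern.** The item is double-barrelled. A dressing can stay where it was put and still leak through, or shift without leaking, and a single rating does not record which of these the subject had in mind. Under section 6.3.2 every participant must have an exuding lesion that needs dressing, so leakage is a live issue for all of them.

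What is at stake is how the retention claim is read. A better pad could raise the score with no gain in retention, and a worse one could hide a real gain. Section 7.1 says the pilot is meant to supply estimates of effect and variability for a full-scale study, so a mixed score would carry forward into that design.

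**Working it through.** The plan gives no standard deviation, effect size or margin for this endpoint. The 0.18 margin of error in section 7.2 concerns the primary response, so there is no figure to reproduce here. The check is mainly a comparison of texts.

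**1. Is there another measure that separates the two?**
- Subject forms (Appendices 3 and 4): one joint item each.
- Nurse forms (Appendix 5): contortion, assistance, raising the arms and additional equipment. Neither displacement nor leakage is recorded.
- Daily check-in (6.1.4, Appendix 7): temperature, number of dressings used and free comments. A dressing count does not say why a dressing was changed, and comments are not scored.

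So nothing else that is scored separates movement from leakage.

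**2. Can the pad influence the score independently of the garment?**
- The dressing is a separate off-the-shelf component of a three-part system (2.1), and the warnings in 2.4 say that the garment is not itself a wound dressing.
- The comparator is the subject's own product at Day 0 (6.2). After that the study supplies dressings for three weeks (12).
- The risk tables in 4.1.1 list leaking or falling off under the supplied dressing as well as under the garment.

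Pad and fixation therefore change together between Day 0 and Day 21, and the plan's own risk tables allow leakage to arise from either.

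**3. What the joint score does, by assumption only.** Let M be the change in confidence about position, L the change in confidence about leaking, and w the weight the subject gives to position, taken as the same on both days. Then:

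item change = w × M + (1 − w) × L

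Only the left-hand side is recorded. All values of M, L and w below are assumed.

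| M | L | w = 0 | w = 0.5 | w = 1 |
|---|---|---|---|---|
| 0 | +1 | 1 | 0.5 | 0 |
| 0 | +2 | 2 | 1.0 | 0 |
| 0 | +3 | 3 | 1.5 | 0 |
| +3 | +2 | 2 | 2.5 | 3 |
| +3 | −2 | −2 | 0.5 | 3 |

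The first three rows show the item moving with no change in retention unless the subject ignores leakage altogether. The last two show that the ambiguity is small when both parts move together and large when they move apart. The documents do not say which to expect.

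**The case against.** The strongest reply is that the plan treats leaking as part of the retention problem. Section 2 groups leaking, moving and falling off as one complaint about current dressings, and 4.1.1 lists leaking under the garment as well as the pad. The comparison is also between systems: the garment with its supplied dressing and fastener against whatever the subject used before. As a rating of the whole system the item remains usable. All of that stands, and a reader who inferred that leakage is purely a pad effect would go beyond the documents. It does not remove the difficulty, because two ratings would show whether leaking and moving change together and one cannot.

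Three other stronger readings are tempting and are not supported:

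- **That the plan defines retention in conflicting ways.** It names retention without defining it. The survey is an anonymous precursor and does not score the 6.1.3 endpoint. Leaving falling off out of the study forms adds little, since a dressing that falls off has moved.
- **That section 3.4 puts leakage outside the assessment.** It says "The clinical effect of the wound pad will not be assessed", but the next sentence disclaims wound healing, so healing is most naturally what is excluded.
- **That the ambiguity exceeds sampling error.** At n = 23 the 95% half-width of a mean change is t(0.975, 22)/√23 = 0.432 SD, or 0.432 × 2.5 = 1.08 points at an assumed SD of 2.5. The +3/−2 row has a spread of 3 − (−2) = 5 points, the +3/+2 row only 3 − 2 = 1 point. The comparison turns on the values chosen, and it sets possible readings of one response against the precision of a mean.

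**Conclusion.** The point holds as one of interpretability. The retention endpoint rests on a single item with two parts, nothing else scored separates them, and pad and fixation change at the same time. A change from Day 0 to Day 21 therefore cannot show whether the retention claim reflects a dressing that stays in place or one that leaks less. The shift in what the item names, from the current dressing to HidraWear AX, adds a smaller inconsistency.

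The weight is minor to moderate. This is one of several secondary endpoints in a single-arm pilot with no power calculation (6.1.1, 7.3), but it supports a claim listed in 5.3. The conclusion rests on the text of the forms and on leakage being able to depend on the pad as well as on position. It does not rest on the illustrative values.

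A reader might also infer that separate items would isolate the garment's contribution. They would not: the supplied pad and fastener are part of the Day 21 system and could affect movement too.

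**What to change.** At Days 0, 7, 14 and 21, replace the joint item with two on the same scale, each naming the dressing as its object on every form:

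- (a) confidence that the dressing will stay in place, meaning that it will not move or fall off;
- (b) confidence that the dressing will not leak.

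In 6.1.3, make (a) the retention endpoint and the basis for the 5.3 claim, and report (b) beside it. Describe both as properties of the whole system (garment, supplied dressing and fastener) against the subject's usual product. Add the Day 7 and Day 14 wording to the appendices. If the comparison with survey data in 3.1 is kept, use matching wording in survey question 13.

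The cost is one extra rating per assessment and small edits to the forms and to 6.1.3. The joint content is not lost, because both parts are reported.

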CE-GAX001-01

V4.0

CR: 144

Date: _____

HidraWear AX HS Study Protocol ID: CE-GAX-001-01 V4 NCT:04449354

Initial Release Date: 18th October 2019

Signed: _____

Sponsor Name: HidraMed Solutions Ltd.

Sponsor Address: [name]

Date:

HidraMed Solutions Ltd.

Signed: _____

Chief Investigator

This document contains confidential and proprietary information and may not be copied or reproduced in whole or part without the written permission of HidraMed Solutions Ltd.

CE-GAX001-01

V4.0

CR: 144

Clinical Agreement Signature Log

I, the undersigned, have read and understand the Clinical Investigation Plan (CIP), and agree to conduct the investigation as stipulated.

The CIP, the Investigator Agreements and any additional information provided by the sponsor will serve as a basis for co-operation in the study.

I will provide copies of the CIP and all pertinent information to all individuals responsible to me who assist in the conduct of this study. I will discuss this material with them to ensure they are fully informed regarding the device and the conduct of the study.

I will use only the informed consent form approved by the Ethics Committee (EC) and will fulfil all responsibilities for submitting pertinent information to the EC.

Principal Investigator:		
Signature	Date	

Name, address and professional position of Principal Investigator:

[name]. Consultant in Rheumatology and General Medicine.

Hermitage Medical Clinic, [name]

CE-GAX001-01

V4.0

CR: 144

Clinical Investigation Summary

Title	HidraWear AX Pilot Study			
Investigational Product	HidraWear AX			
Introduction	The product, HidraWear AX is and adhesive free wound dressing system for the every day home care of Hidradenitis Suppurativa (HS), a debilitating disease of the skin for which there are limited wound dressing products.			
	This is a study to assess the use HidraWear Ax vs current product and method of use.			
Study Objectives:				
	The objective is to evaluate the ease of use of Hidrawear AX compared to the subject's existing product use in 23 subjects with HS (Hidradenitis Suppurativa).			
	Secondary objectives are to evaluate if Hidrawear AX:			
	Is comfortable			
	Improves quality of life			
	Faster to use than the subject's existing product			
	Reduces dressing related pain			
	Secure dressing retention			
Study Design:	Sample size: 23			
	Female, over 18, presenting with HS of the axilla			

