2.4 Contraindications and Warnings

A full list of contraindications and warnings are provided in the IFU supplied with the device.

Contraindications: Known allergies to materials specified

Warnings: Do not use if you have known allergies to materials specified.

Warnings

- 1. The garment is not a wound dressing wound(s) should be fully covered by dressing(s).
- 2. If any unexpected discomfort or wound irritation occurs, please consult your doctor or nurse.
- 3. Do not use, if you have a known allergy or sensitivity to materials listed.

CE-GAX001-01

V4.0

CR: 144

Potential side effects: Dermatitis, infection and skin irritation or skin abrasion.

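### Day 21 item 13 can be read as a question about the garment, while Day 0 item 6 asks about the dressing, so the object of the retention comparison is ambiguous

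*Combined protocol and SAP*

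**What the plan says.** Section 6.1.3 lists the secondary endpoint "Dressing retention confidence measured on a 10 point scale D21 vs D0". Two form items supply it:

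- Day 0, Appendix 3, item 6: "How confident are you that your current dressing will not leak or move".
- Day 21, Appendix 4, item 13: "How confident are you that HidaWear AX will not leak or move" (product name spelled as on the form; the spelling is immaterial).

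Before the items, both forms list what the subject should notice while dressing the wound, including "How confident are you that your dressing will not leak or move". The Day 21 form opens with "Please dress your wound using HidraWear AX".

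The protocol uses the product name in two senses. Section 2.1 describes a three-part system and lists as its first part "The investigational device: the Hidrawear AX: A washable garment"; the dressing and the means of attaching it are the other two parts. Section 2.4 warns "The garment is not a wound dressing". Section 2.3 gives the intended purpose as holding a dressing in the axilla, and section 4.5 says that the study assesses the garment. The Clinical Investigation Summary, by contrast, says "HidraWear AX is and adhesive free wound dressing system for the every day home care of Hidradenitis Suppurativa (HS".

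Section 5.3 lists secure retention of the dressing among the performance claims.

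**The concern.** A change from Day 0 to Day 21 can be interpreted only if the same thing is rated on both days. If HidraWear AX means the garment, item 13 asks whether the retaining device moves, while item 6 asks whether the retained dressing moves. A subject whose pad slips under a garment that stays in place could truthfully report high confidence on item 13.

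The item matters more than one secondary rating usually would, because no other appended item directly rates retention under HidraWear AX. The nurse forms (Appendix 5) have no retention question. The daily check-in (Appendix 7) covers only temperature, number of dressings used and comments. The study is single-arm and unblinded (section 6.1.1), so nothing else in the appended forms would reveal a distortion in the rating behind this performance claim.

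**Working it through.** No sample size, power or precision figure rests on the retention item, so there is no plan figure to reproduce. The margin of 0.18 in section 7.2 refers to the primary response. The check is a comparison of wording, followed by an illustration of the possible shift.

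**Step 1. Set the paired items side by side** (Appendix 3 against Appendix 4).

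| Topic | Day 0: object | Day 21: object | Same object? |
|---|---|---|---|
| Ease of use | item 1: changing the dressing | item 8: changing the dressing, with HidraWear AX | yes |
| Time | item 2: a dressing change | item 9: a dressing change, with HidraWear AX | yes |
| Comfort | item 3: the current dressing | item 10: HidraWear AX | depends on the definition |
| Pain | item 5: dressing-related pain | item 12: dressing-related pain, with HidraWear AX | yes |
| Retention | item 6: the current dressing | item 13: HidraWear AX | depends on the definition |

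Items 8, 9 and 12 name the new product and still keep the dressing, or the dressing change, in the question. Naming the product therefore did not require dropping the dressing from item 13. Comfort items 3 and 10 shift in the same way, so the problem is not confined to retention.

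**Step 2. Apply each definition to item 13.** Under the garment sense, the object changes between visits. Under the system sense, it does not, because the system includes the dressing. The protocol supports both senses, so the item is ambiguous.

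**Step 3. Check the other occasions.** Section 6.1.4 and Appendix 7 say that confidence is also asked by emailed link on Days 7 and 14. No wording for that survey is appended, so neither its object nor the presence of the lead-in can be confirmed. Section 3.1 also plans a comparison with the online survey. Its retention question (Appendix 2, section 3, item 13) concerns current dressings, so its object is the dressing too.

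**Step 4. Illustrate the shift.** Let q be the share of subjects who rate the garment and s the extra points they give compared with rating the dressing. Both are assumptions; the documents give neither. The shift in the mean Day 21 minus Day 0 difference is q × s.

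| | s = 1 | s = 2 |
|---|---|---|
| q = 0 | 0 | 0 |
| q = 0.25 | 0.25 × 1 = 0.25 | 0.25 × 2 = 0.5 |
| q = 0.5 | 0.5 × 1 = 0.5 | 0.5 × 2 = 1.0 |
| q = 1 | 1 × 1 = 1.0 | 1 × 2 = 2.0 |

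If some subjects do misread the item (q from 0.25 to 1), the range is 0.25 to 2.0 points on the 10-point scale. If none do, it is zero.

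**The case against.** The strongest reply is that context settles the meaning. The Day 21 form tells the subject to dress her wound with HidraWear AX, so the name stands for whatever the wound is dressed with. The lead-in names the dressing in the same words on both days. Section 6.1.4 gives the same construct at both visits, and section 3.4 presents the product as a way to dress wounds. Leakage also points to the part that holds exudate: a subject whose pad leaks is unlikely to say that nothing leaked. Finally, some change of name is unavoidable when a subject's own product is compared with a new one.

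Much of this stands. It makes misreading less likely, and it rules out saying that two different questions are certainly being subtracted. A reader might infer that from section 2.1 alone, but the Clinical Investigation Summary and the shared lead-in do not support it. Two points remain. The lead-in tells the subject what to notice, whereas the recorded answer is to item 13. And the neighbouring items show that the dressing could have been kept in the question.

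A reader might also infer that the wording alone could produce an apparently clear benefit. Suppose one third of subjects score 3 points higher: the shift is (1/3) × 3 = 1.0. With an assumed SD of change of 2 and n = 23, the 95% half-width is t(0.975, 22)/√23 × 2 = 0.432 × 2 = 0.86, which is below 1.0. That result is fragile:

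- With an SD of 2.5 the half-width is 0.432 × 2.5 = 1.08.
- With the six anticipated drop-outs not replaced (n = 17) and an SD of 2, it is t(0.975, 16)/√17 × 2 = 0.514 × 2 = 1.03. Section 6.3.6 does allow replacement.
- With q = 0.25 and s = 2, the shift is 0.5, inside 0.86.

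The documents supply none of the share, the extra points or the SD. Nor do they give data showing that the garment moves less than a pad.

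**Conclusion.** The point holds as an ambiguous referent in item 13, not as a demonstrated bias. Some subjects could rate the garment, and this may distort the change in dressing retention confidence. A shift in favour of HidraWear AX is plausible for movement and less clear for leakage. Its size cannot be computed from the documents; the range in the working depends wholly on the assumed share and score difference. The response scales are not shown in the available text, so anchors that might name the dressing could not be checked.

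The effect is limited to a secondary endpoint and the performance claim resting on it, with a similar question over comfort. The primary endpoint (ease of use) keeps its object across visits, and the sample size was chosen on feasibility. This is a low-cost improvement to a pilot, worth making before data collection because wording cannot be repaired once the answers are in.

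**What to change.** 1. Keep the dressing as the object on every occasion. Reword item 13 to: *How confident are you that your dressing, held in place by HidraWear AX, will not leak or move?*
2. Use that wording in the Day 7 and Day 14 surveys, and append those surveys to the protocol.
3. Give comfort items 3 and 10 parallel objects.
4. Choose one definition of HidraWear AX, garment or system, and use it throughout the protocol and forms.

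The cost is a few lines on the forms, consistent terminology in the text, and the ethics committee review that the protocol requires for any amendment. No extra visits, subjects or data are needed.
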